2.2 Secondary Endpoints

- 2.21 To evaluate the EOI overall response rate (ORR) for the combination of RSc+Pola+Ven in relapsed/refractory MCL.
- 2.22 To evaluate the best response (CR, PR) in patients who continue on to maintenance therapy and evaluate the improvement in the depth of response.
- 2.23 To evaluate the progression free survival (PFS) and overall survival (OS) for the combination of RSc+Pola+Ven in relapsed/refractory MCL.
- 2.24 To compare the ORR, CR, PFS, and OS in ibrutinib refractory compared to ibrutinib naïve patients.

2.25 To evaluate regimen-related toxicity for patients treated with RSc+Pola+Ven.

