¹⁸ Subjects must return to the consenting ACCRU institution for CBC evaluation, or have outside laboratory CBC every 7 days during the first 6 weeks of therapy

¹⁹ Tissue is to be submitted no more than 30 days *after* registration. See Section 17.0 for more details.

^R Research funded

² Progressive disease is based on either PET-CT based or CT based response criteria

NOTE: A +/-14 day window is allowed for all survival follow-up visits.

5.0 Grouping Factors:

- 5.1 Cohort: Safety portion vs. expansion portion
- 5.2 Venetoclax Dosing Safety Lead-In: Dose 0 vs Dose -1
- 5.3 Previous ibrutinib exposure: ibrutinib naïve vs. ibrutinib pre-treated

NOTE: To ensure equal distribution of both ibrutinib naïve and pretreated patients at the dose level determined during the safety run-in, a minimum of 25 patients must be ibrutinib naïve. Therefore, accrual of ibrutinib pretreated patients will stop after 26 Ibrutinib pretreated patients are accrued

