16.0 Statistical Considerations and Methodology

16.1 Overview:

This is a single arm Phase II study of combination of polatuzumab vedotin, venetoclax

and rituximab and hyaluronidase human in patients with relapsed or refractory mantle cell lymphoma (MCL). The relapsed/refractory MCL patient population will include both ibrutinib-naive and ibrutinib-pretreated patients. An early safety analysis will be conducted in patients with B cell NHL who have relapsed or progressed after at least one line of therapy prior to continuing accrual in this phase II study.

16.11 Primary Endpoint: The primary endpoint of this trial is the complete response rate at the end of induction by PET-CT scans according to Lugano 2014. A complete response will be considered synonymous with "success", unless specified otherwise. All patients meeting the eligibility criteria, who have signed a consent form and have begun treatment, will be evaluable for response, unless they are determined to be a major violation.

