- 16.22 Sample Size: The one stage design with an interim analysis to be utilized is fully described above. A minimum of 16 and a maximum of 46 evaluable patients with MCL will be accrued onto this phase II study unless undue toxicity is encountered. Patients with MCL treated at the final dose level in the early safety analysis will be included in phase II. If dose de-escalation is required during the safety analysis, an additional 6 evaluable patients will be accrued per section 16.4. We anticipate accruing an additional 5 (10%) patients to account for ineligibility, cancellation, major treatment violation, or other reasons for a total of up to 57 patients. If none of the six patients with B cell NHL enrolled in safety portion are MCL, the total sample size will be 63 patients.
- 16.23 Accrual Rate and Study Duration: The anticipated accrual rate is 2-3 evaluable MCL patients per month. At this rate, it will likely take about 2 years to enroll the patients. The maximum total study duration is expected to be approximately 5 years, or until the last patient accrued has been observed for at least 3 years. The earliest date anticipated for presentation of results is at approximately 2.5 years for the primary endpoint, or when the last patient accrued has been observed for at least 6 months.
- 16.24 Power and Significance Level: Assuming that the number of successes is binomially distributed, the significance level is .05, i.e. there is a 5% chance of finding the drug to be effective when it truly is not. The probability of declaring that this regimen warrants further study (i.e. statistical power) and the probability of stopping at the interim analysis under various success proportions can be tabulated as a function of the true success proportion as shown in the following table.

If the true success proportion is	0.15	0.20	0.25	0.30	0.35
Then the probability of declaring that the regimen warrants further studies is	0.049	0.212	0.467	0.700	0.851
And the probability of stopping at the interim analysis is	0.790	0.598	0.405	0.246	0.134

16.25 Other Considerations: AEs, quality/duration of response, and patterns of treatment failure observed in this study, as well as scientific discoveries or changes in standard care will be taken into account in any decision to terminate the study.

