16.31 Primary Outcome Analysis

- 16.311 Definition: The primary endpoint of this trial is the complete response rate at the end of induction as determined by investigator on the basis of PET-CT scans according to Lugano 2014. A complete response is defined as an objective status of CR at the end of induction. All patients meeting the eligibility criteria who have signed a consent form and have begun treatment will be evaluable for response, unless they are determined to be a major violation. Only MCL patients treated at the final dose level will be included when evaluating the decision rules in Sections 16.211 and 16.212. Patients without MCL and patients treated at other dose levels will be summarized separately.
- 16.312 Estimation: The proportion of success will be estimated by the number of success divided by the total number of evaluable patients. 95% confidence intervals for the true success proportion will be calculated according to the approach of Duffy and Santner³.
- 16.313 Over Accrual: If more than the target number of patients are accrued, the additional patients will not be used to evaluate the stopping rule or used in any decision-making process; however, they will be included in final point estimates and confidence intervals.

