16.32 Secondary Outcome Analysis

- 16.321 The overall response rate (ORR) at the end of induction will be estimated by the total number of patients who achieve a CR or PR by PET-CT scans according to Lugano 2014 divided by the total number of evaluable patients. All evaluable patients will be used for this analysis. Exact binomial 95% confidence intervals for the true overall response rate will be calculated. The ORR between ibrutinib-naive and ibrutinib-pretreated patients will be compared using Fisher's exact test.
- 16.322 The Best Response Rate to maintenance therapy will be evaluated. CR, PR and SD rates for patients who continue to maintenance will be estimated by number of patients who continue on maintenance therapy and achieve CR, PR or SD, respectively, at the end of maintenance divided by the total number of evaluable patients who continue to maintenance. Conversion rate from PR to CR will be evaluated by the number of patients achieving CR at EOM divided by the total number of patients who continue to maintenance in PR. Conversion rate from SD to PR or SD to CR will be evaluated by the number of patients achieving PR or CR, respectively at EOM divided by the total number of patients who continue to maintenance in SD.
- 16.323 Progression free survival (PFS) is defined as the time from registration to the earliest date of documentation of disease progression by CT or

- PET/CT or death due to any cause. The distribution of progression-free survival will be estimated using the method of Kaplan-Meier⁴. The PFS between ibrutinib-naive and ibrutinib-pretreated patients will be compared using log-rank test.
- 16.324 Overall survival (OS) is defined as the time from registration to death due to any cause. The distribution of OS will be estimated using method of Kaplan-Meier. The OS between ibrutinib-naive and ibrutinib-pretreated patients will be compared using log-rank test.
- 16.325 AEs: All eligible patients that have initiated treatment will be considered evaluable for assessing AE rate(s). The maximum grade for each type of AE from each patient will be used for analysis, and frequency tables will be reviewed to determine patterns. Additionally, the relationship of the AE(s) to the study treatment will be taken into consideration.
- 16.326 Correlative Analysis: Due to the small overall sample size, the results of these analyses will be considered exploratory and hypothesis- generating in nature.

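### Section 16.32 does not deliver objective 2.24: end-of-induction CR is never compared by ibrutinib group, and ORR, PFS and OS are compared for pretreated rather than refractory patients

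*Combined protocol and SAP*

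**What the plan says.** Section 2.2, item 2.24, sets the secondary objective: "To compare the ORR, CR, PFS, and OS in ibrutinib refractory compared to ibrutinib naïve patients".

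The grouping factor in Section 5.3 is exposure: "Previous ibrutinib exposure: ibrutinib naïve vs. ibrutinib pre-treated". Its note controls accrual on the same split: "a minimum of 25 patients must be ibrutinib naïve", and "accrual of ibrutinib pretreated patients will stop after 26 Ibrutinib pretreated patients are accrued". Section 16.1 describes the population in the same terms: "patient population will include both ibrutinib-naive and ibrutinib-pretreated patients".

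The analyses in Section 16.32 follow the exposure grouping. For ORR (16.321): "The ORR between ibrutinib-naive and ibrutinib-pretreated patients will be compared using Fisher's exact test". Sections 16.323 and 16.324 compare PFS and OS between the same two groups by log-rank test.

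For CR at the end of induction, Section 16.312 gives one overall estimate: "The proportion of success will be estimated by the number of success divided by the total number of evaluable patients". Section 16.322 reports CR at the end of maintenance, among patients who continue to maintenance, without an ibrutinib split. The subset analysis in 16.72 concerns race and gender.

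**The concern.** The objective and the analysis section differ in two ways.

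First, an endpoint is missing. CR is named in 2.24 and is the variable on which the trial is judged, yet the plan never compares it by ibrutinib group. The ORR test is no substitute, because ORR pools CR with PR.

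Second, the contrast changes. Refractory describes how the disease behaved on ibrutinib; pretreated says only that the drug was given. Section 1.4 foresees a role for the regimen in BTK-naive or BTK-resistant patients, so the distinction matters to how the trial presents itself. A pretreated-versus-naive result could be reported under an objective that speaks of refractory disease, and a small observed difference could be taken as similar activity in refractory patients, which these tests would not show.

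If nothing changes, whoever writes the report must either leave part of a secondary objective unanswered or choose a definition and a CR analysis after seeing the data.

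**Working it through.** **Objective against plan**

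| Endpoint in 2.24 | Contrast in 2.24 | Planned comparison | Contrast planned |
|---|---|---|---|
| ORR | refractory v naive | 16.321, Fisher's exact test | pretreated v naive |
| CR | refractory v naive | none (16.312 pooled; 16.322 end of maintenance, unsplit) | none |
| PFS | refractory v naive | 16.323, log-rank test | pretreated v naive |
| OS | refractory v naive | 16.324, log-rank test | pretreated v naive |

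One of four endpoints has no comparison, and none of the other three uses the contrast in the objective.

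**Can a patient be pretreated but not refractory?** Section 3.12 offers three routes into the expansion portion: relapse or progression after at least two lines, after one BTK-inhibitor-containing line, or after autologous transplant. A patient who qualifies by two lines or by transplant may have had ibrutinib at some point without failing it, for example having stopped it for intolerance. Even on the BTK route, relapse after a line is not necessarily refractoriness to it. The two groups need not coincide, and no section defines refractory or makes it a grouping factor.

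**The plan's own figures.** The documents give no power for the ibrutinib comparison. The primary design (stop at 3 or fewer CRs in 16; promising at 11 or more in 46) reproduces. The probability of a promising result is 0.0486 at a true CR of 15% and 0.8506 at 35%, against 0.049 and 0.851 in 16.24. Nothing below alters it.

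**Group sizes.** The limits in 5.3 add to 25 + 26 = 51. Section 16.22 gives 46 evaluable patients plus an allowance: "We anticipate accruing an additional 5 (10%) patients to account for ineligibility, cancellation, major treatment violation". 46 + 5 = 51, so accrual is built on the exposure split. If the cap of 26 is reached and all 5 losses fall in one group, the evaluable split is 25 − 5 = 20 v 26, or 25 v 26 − 5 = 21. With no losses it is 25 v 26.

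**Precision of a CR comparison at those sizes.** Assume CR near 35% in both groups; this borrows the design alternative, as the documents give no subgroup rates. Clopper-Pearson 95% intervals are:

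- 7/20 = 35%: 15% to 59%
- 9/26 = 35%: 17% to 56%
- 9/25 = 36%: 18% to 57%
- 7/21 = 33%: 15% to 57%

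Newcombe 95% intervals for the naive-minus-pretreated difference are:

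- 7/20 v 9/26: −25 to +27 percentage points
- 9/25 v 7/21: −24 to +28
- 9/25 v 9/26: −23 to +26

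**Power.** With a two-sided Fisher test at 0.05 (an assumed level), 25 v 26 patients give power 0.33 for 35% v 15% and 0.29 for 45% v 25%. At 23 v 23 the figures are 0.25 and 0.20. A difference of 20 points would usually be missed, so the comparison serves estimation rather than testing.

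**The case against.** The best defence is that the gap is one of wording and consequence is small. These are secondary comparisons with no decision rule. Everything operational in the plan (5.3, 16.1 and 16.32) consistently says pretreated, so 2.24 may simply use a loose word. The overlap may also be large: 3.12 requires relapsed or refractory disease, its BTK route requires relapse or progression after that therapy, and 3.29b provides for patients progressing on ibrutinib. Medical history is collected and the case report forms are not among the documents, so response to earlier ibrutinib may already be captured. Finally, the CR comparison would have low power.

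Much of this stands. It limits the weight of the point and favours rewording 2.24 as the simplest remedy. It does not supply the missing CR analysis, and it does not make the two terms equivalent under 3.12. Low power is not a reason to omit CR when ORR, PFS and OS are compared in the same small groups.

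A reader might go further in two ways that the documents do not support:

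- **That patients who had only another BTK inhibitor, such as acalabrutinib, are misclassified as naive.** Sections 2.24, 5.3 and 16.32 all say ibrutinib naive. Such a patient fits that term, although the plan does not discuss the case. Preferring a contrast by BTK-inhibitor class is a design choice, not a correction of an error.
- **That the use of pretreated dilutes the effect by a calculable amount.** The documents give neither the share of exposed patients who are non-refractory nor any response rate by group, so no percentage can be justified.

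**Conclusion.** The point holds as an inconsistency between objective and analysis that should be corrected. The planned tests do not deliver 2.24 as worded: end-of-induction CR by ibrutinib group is absent, and ORR, PFS and OS are compared by exposure while the objective names refractory disease without defining it.

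The consequence is confined to a secondary objective and its interpretation; the primary decision rule, error rates and sample size do not change. How far pretreated and refractory differ in this trial cannot be known from the documents. The precision figures rest on the 26-patient cap being reached, up to 5 losses, and an assumed CR near 35% in both groups. If fewer pretreated patients enrol, the groups would be less balanced than shown.

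**What to change.** 1. **One contrast.** Change 2.24 to ibrutinib pretreated compared with ibrutinib naive, matching 5.3 and 16.32, and draw no conclusion about refractory disease from these tests. Alternatively, if refractory disease is the intended question, define it prospectively, record it at registration, and make refractory versus naive the stated contrast in 2.24 and 16.32, with pretreated versus naive as supportive.
2. **Add CR.** In 16.32, report end-of-induction CR by ibrutinib group with exact 95% confidence intervals for each group and Fisher's exact test, labelled descriptive.
3. **Optional refinement.** Record the prior BTK inhibitor by name and, as a sensitivity analysis, report separately any patients exposed only to a BTK inhibitor other than ibrutinib.

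The cost is a wording change, a small added analysis and, if refractory is kept, a definition and one registration item. Keeping refractory also makes the exposed group in the main contrast smaller by an unknown number. The optional step adds one data item unless the agent is already captured. Accrual limits and visits stay as they are, and the CR comparison remains a low-powered secondary result.

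### Section 16.321: Fisher's exact test for the ORR comparison by ibrutinib history is valid but conservative; an unconditional exact test with an interval for the difference would be a free improvement

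*Combined protocol and SAP*

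**What the plan says.** Section 2.2 lists the subgroup contrast among the secondary goals: "To compare the ORR, CR, PFS, and OS in ibrutinib refractory compared to ibrutinib naïve patients". Section 16.321 implements the ORR part: "The ORR between ibrutinib-naive and ibrutinib-pretreated patients will be compared using Fisher's exact test". On the analysis set it says "All evaluable patients will be used for this analysis". It plans an exact binomial 95% interval for the true overall response rate. It names no difference between the groups, no interval for one, and no level, sidedness, effect size or power for the comparison.

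Group sizes are governed by two rules. Section 5.3 requires that "a minimum of 25 patients must be ibrutinib naïve" and that "accrual of ibrutinib pretreated patients will stop after 26 Ibrutinib pretreated patients are accrued". Section 16.22 states: "A minimum of 16 and a maximum of 46 evaluable patients with MCL will be accrued onto this phase II study", with an allowance: "We anticipate accruing an additional 5 (10%) patients to account for ineligibility, cancellation, major treatment violation, or other reasons". The quota therefore matches 46 + 5 = 51 accrued patients as 25 + 26.

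The only significance level in section 16 is in 16.24: "the significance level is .05, i.e. there is a 5% chance of finding the drug to be effective when it truly is not". It belongs to the single-arm CR decision rule.

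**The concern.** The number of responders in each group is random, so the comparison is one of two independent binomials. Fisher's test conditions on the total number of responders as well. With a little over 20 patients per group, few tables are possible for each total, and the attainable error rate falls below the nominal one. Power is given up without any gain in protection.

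The sponsor shaped accrual around these two groups, and the rationale in section 1.4 looks ahead to use in both BTK-naive and BTK-resistant patients. A non-significant result is the likely outcome even if activity differs substantially. If it is reported as a p-value alone, a reader may take it as evidence that activity is the same.

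**Working it through.** **The plan's own figures.** None exists for this comparison. The table in 16.24 for the CR rule (stop at 3 or fewer of 16; success at 11 or more of 46) reproduces by exact enumeration. At a true rate of 15%, P(declare active) is 0.0486 and P(stop early) is 0.7899, against the stated 0.049 and 0.790. At 35% they are 0.8506 and 0.1339, against 0.851 and 0.134.

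**Inputs**
- From the documents: Fisher's exact test (16.321); at least 25 naive and at most 26 pretreated accrued (5.3); at most 46 evaluable MCL patients plus an allowance of 5 (16.22).
- Assumed: a two-sided 5% level.
- Assumed: ORR pairs of 80% v 50%, 85% v 55%, 90% v 60% and 80% v 60%. The documents give no subgroup ORRs.
- Assumed: the evaluable split. If all 25 naive patients are evaluable, 46 - 25 = 21 are pretreated. A 23 v 23 split with exactly 25 naive accrued needs 25 - 23 = 2 of them to be non-evaluable. Splits of 24/23 (47) and 25/26 (51) exceed 46 and arise only if extra patients prove evaluable. A 30/16 split is also allowed, because 5.3 sets no ceiling on naive patients and no floor on pretreated ones.

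**Method.** For group sizes n1 and n2 and rejection region R (the set of tables x, y that are declared significant):
- Power = sum over R of Bin(x; n1, p1) × Bin(y; n2, p2).
- Maximum size = the largest value of that sum when p1 = p2, over common rates 0.001 to 0.999.
- Fisher: R is every table with a two-sided Fisher p-value of at most 0.05.
- Boschloo: R is every table with a two-sided Fisher p-value at or below a cut-off c, where c is the largest value that keeps the maximum size at or below 0.05. At 23 v 23, c = 0.0746; at 20 v 26, c = 0.0701. Because c is above 0.05, R contains Fisher's region, so power cannot fall.

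**Power at 23 v 23** (maximum size: Fisher 2.60%, Boschloo 4.75%)

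| ORR pair | Fisher | Boschloo | Gain (points) |
|---|---|---|---|
| 80% v 50% | 46.2% | 56.1% | 9.9 |
| 85% v 55% | 50.7% | 58.5% | 7.8 |
| 90% v 60% | 57.5% | 63.6% | 6.2 |
| 80% v 60% | 22.1% | 28.5% | 6.4 |

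Gains are taken before rounding.

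**Other splits, same four pairs**

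| Split | Fisher maximum size | Boschloo gain (points) |
|---|---|---|
| 22/24 or 24/22 | 3.9% | 5.1 to 7.2 |
| 25/21 | 3.5% | 6.3 to 7.8 |
| 20/26 or 26/20 | 3.7% | 4.4 to 6.9 |
| 25/26 | 3.8% | about 4 to 6 |
| 24/23 | 4.0% | 2.0 to 3.5 |
| 30/16 (30 naive, higher ORR in naive) | 3.75% | 0.1 to 2.8 |

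**Wider range of ORRs.** The grid took the higher rate from 60% to 95%, the lower from 30% upward and a difference of at least 20 points, and kept pairs where Fisher's power is 20-90%. The median Boschloo gain is 7.5 points at 23/23, 2.4 at 22/24, 3.2 at 25/21, 3.9 at 20/26 and 4.5 at 25/26.

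**What a p-value alone would hide.** Suppose both groups show an ORR near 70% with 23 patients each. The simple 95% interval for the difference has half-width 1.96 × sqrt(2 × 0.70 × 0.30 / 23) = 1.96 × 0.135 = 0.265. An observed difference of zero would still be compatible with a true difference of about 26 points in either direction.

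**The case against.** Fisher's test is pre-specified, familiar and keeps the error rate at or below nominal. Choosing between a conditional and an unconditional exact test is choosing between two acceptable methods. The comparison is secondary, carries no stated power and enters no decision rule, since those rules use CR alone. It remains underpowered with either test, so changing the test does not by itself prevent a null result from being over-read. All of that stands. It limits the importance of the point, but it does not remove a gain that costs nothing.

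A reader might infer something stronger: that the quota fixes the groups at about 23 v 23, that Fisher's true error rate is therefore half the nominal 5%, and that 5-10 points of power are lost. The documents do not support this. They never give a 23 v 23 split; they give a minimum of 25 naive and a maximum of 26 pretreated patients accrued. The halved error rate is peculiar to that exactly equal split: moving one patient, to 22/24, raises Fisher's maximum size from 2.6% to 3.9%. The gain also depends on subgroup ORRs that the documents do not give.

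Nor is it fair to say that 16.321 offers only a p-value. It plans an interval for the overall ORR. What it lacks is an estimate and interval for the difference, and adding these does not depend on which test is used.

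**Conclusion.** The point holds as an optional efficiency gain, not as an error in the plan. With an assumed two-sided 5% level, Fisher's maximum true size is about 2.6% at 23 v 23 and about 3.5-4.0% at the nearby unequal splits. Under the four assumed ORR pairs, Boschloo's test gains 6-10 points at 23/23, about 4-8 at 22/24, 25/21 and 20/26, 2-3.5 at 24/23, and under 3 at 30/16. It never loses power or exceeds 5% size.

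The more useful half of the point is the missing interval. Even with the better test, power to detect 80% v 50% at 23 v 23 is only 56%, so the size of difference still compatible with the data should be shown. Importance is low, because no decision rule uses this comparison.

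**What to change.** In 16.321, replace Fisher's exact test with Boschloo's unconditional exact test at two-sided 5%. Define it by ordering tables on the two-sided Fisher p-value, since the guarantee of never losing power relies on that definition. Add that the ORR difference (naive minus pretreated) will be reported with a 95% confidence interval beside the p-value, and name the interval method. Make the change before the data are seen; a test chosen afterwards would not be credible.

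The cost is a sentence or two of text. It needs no extra patients, data or visits, and error control is unchanged. If the team prefers to keep Fisher's test, the interval should be added anyway.
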